Administrative Letter 10	30-Apr-2018	
Updated EUDRACT number and UTN.
 
Deleted Exclusion Criteria 2., j), ii) and iii)
 
In Table 5.1-7, in Cohort B, corrected every 4 cycles to start at cycle 9 instead of 11.

Revised Protocol 14	15-Feb-2018	
Major changes:
 
 • In compliance with requests from the FDA, enrollment into the nivolumab +daratumumab with and without pomalidomide (ND±Pd: Cohort A) has been stopped. Cohort B (nivolumab +daratumumab vs daratumumab monotherapy [ND, D]) has been opened, with at 2:1 randomization. 
 ○ Eligibility changes to the patient population for patients to be enrolled in Cohort B and toxicity stopping rules for the ND arm have been incorporated. ○ Cohort B patients (only) treated in the ND arm: Dose regimen change: nivolumab 480 mg every 4 weeks (Day 1) will begin at Cycle 2 rather than at Cycle 7 and continue until the end of treatment. Cycle 1 dose: 240 mg on Day 15. • The biomarker assessments have been aligned to the multiple myeloma program wide biomarkers evaluations. • All content related to the nivolumab +ipilimumab combination has been removed because all study procedures for this cohort, including follow-up evaluations, have been completed. 
Of note, Revised Protocol 13 was not activated at the study sites.
 
All changes are further detailed in the Summary of Key Changes.

Document	Date of Issue	Summary of Changes
Revised Protocol 13	04-Aug-2017	
Major changes are corrections and updates pertinent only to the nivolumab/daratumumab cohorts as follows:
 
 • Changes in eligibility for subjects with multiple myeloma (MM) for enrollment in the nivolumab/daratumumab cohorts include: 
 – Eligible subjects must have failed prior treatment with an immune modulatory drug (IMiD) and/or a proteasome inhibitor (PI) rather than the requirement of failure to treatment with both prior treatment types. Refractory and relapsed refractory definitions removed as criterion definitions. – Subjects who received prior treatment with pomalidomide are no longer excluded from eligibility. • The randomization ratio has been changed to a 2:1 ratio, which increases the nivolumab + daratumumab + pomalidomide (ND-Pd) regimen cohort to 40 and reduces the nivolumab + daratumumab (ND) regimen cohort to 20. The sample size calculation has been updated to support change in randomization ratio. • Changes to the biomarkers plan were made to align with the program level approach and small corrections were made to the biomarkers collections schedule to ensure consistency throughout the protocol. In addition, Biomarker collections from peripheral blood specimens have been clarified to remove duplicate collections. • Daratumumab specific requirements for dose delays and discontinuation, drug preparation and administration, prevention and management of infusion related reactions, and permitted and restricted treatments have been aligned with the daratumumab IB and daratumumab standard protocol elements.
Administrative Letter 07	21-Jul-2017	Corrected inclusion criteria for subjects with MM in the nivolumab/daratumumab cohorts to accurately specify prior use of antimyeloma therapy.
Administrative Letter 06	09-Mar-2017	Corrected error on Biomarker Sampling Schedule Table 5.1-6
Revised Protocol 12	19-Jan-2017	Incorporates Amendment 13
Amendment 13	19-Jan-2017	This amendment includes corrections and updates pertinent only to the nivolumab/daratumumab cohorts. Additional biomarkers evaluations from peripheral blood specimens have been included. Daratumumab specific requirements for eligibility, dose delays and discontinuation, drug preparation and administration. Prevention and management of infusion related reactions, and permitted and restricted treatments have been aligned with the daratumumab IB and daratumumab standard protocol elements.
Administrative Letter 05	22-Nov-2016	Corrected Schedule of Assessment to align with Section 5.2.1.2 for IMWG response and provided clarification for location of bone marrow samples.
Administrative Letter	18-Oct-2016	Corrected errors in exclusion criterion for QTC prolongation and

Document	Date of Issue	Summary of Changes
04		platelet count in criteria to resume treatment with daratumumab.
Administrative Letter 03	23-Aug-2016	Clarification for inconsistencies between the age groups for dexamethasone dosing defined in the dosing schema and in protocol body, and to provide details for specific bone marrow assessments included in the IMWG response criteria.
Revised Protocol 11	09-Aug-2016	Incorporates Amendment 12
Amendment 12	09-Aug-2016	Adds an additional set of cohorts (approximately 60 additional subjects) for dose expansion in multiple myeloma patients treated with Nivolumab and Daratumumab with or without Pomalidomide and Dexamethasone
Administrative Letter 02	03-Feb-2016	Change in Study Director/Central Medical Monitor
Revised Protocol 10	01-Oct-2015	Incorporates Amendment 11
Amendment 11	01-Oct-2015	Update follow up requirements
Revised Protocol 09	15-Apr-2015	Incorporates Amendment 10
Amendment 10	15-Apr-2015	Retrospectively collect radiographic images for blinded independent central review
Revised Protocol 08	05-Feb-2015	Incorporates Amendment 09
Amendment 09	05-Feb-2015	Removes exploratory cohorts from the nivolumab/ipilimumab cohorts
Revised Protocol 07	02-Dec-2014	Incorporates Amendment 08
Amendment 08	02-Dec-2014	Revises protocol to meet FDA guidance.
Revised Protocol 06	20-Aug-2014	Incorporates Amendment 07
Amendment 07	20-Aug-2014	Adds an additional set of cohorts (approximately 80 additional subjects) for dose expansion with combination of lirilumab and nivolumab
Revised Protocol 05	19-Dec-2013	Incorporates Amendment 06
Amendment 06	19-Dec-2013	Adds an additional set of cohorts (approximately 75 additional subjects) for dose escalation and dose expansion with combination of ipilimumab and nivolumab.
Revised Protocol 04	10-Oct-2013	Incorporates Amendment 05
Amendment 05	10-Oct-2013	Includes corrections for protocol clarity.
Revised Protocol 03	25-Jun-2013	Incorporates Amendment 04
Amendment 04	25-Jun-2013	Eliminate the CML cohort in the expansion phase as recruitment would be difficult due to lack of concomitant therapy with a tyrosine kinase inhibitor and increase the size of the remaining four cohorts from 16 to 23 subjects to redistribute the allotted patients from the eliminated CML cohort.
Revised Protocol 02	06-Mar-2013	Incorporates Amendment 03
Amendment 03	06-Mar-2013	Inclusion of non-clinical safety findings related to reproductive toxicology data

Document	Date of Issue	Summary of Changes
Revised Protocol 01	21-Dec-2012	Incorporates Administrative Letter 01 and Amendment 02
Amendment 02	21-Dec-2012	Eliminate the highest (10 mg/kg) of three dose levels scheduled to be examined, require that 8 of 16 subjects with multiple myeloma be required to undergo bone marrow biopsy while on therapy, and modify the discontinuation criteria to be more stringent
Administrative Letter 01	23-May-2012	Update Medical Monitor
Original Protocol	13-Mar-2012	Not applicable

SYNOPSIS

Clinical Protocol CA209039

Protocol Title: Multiple Phase 1/2 Cohorts of Nivolumab Monotherapy or Nivolumab Combination Regimens Across Relapsed/Refractory Hematologic Malignancies

Investigational Product(s), Dose and Mode of Administration, Duration of Treatment with Investigational Product(s):

BMS-936558 (nivolumab)

- Flat dose regimen: Intravenous (IV) infusion of BMS-936558 (nivolumab) at dose of 240 mg every 2 weeks (Q2W) in Cycles 1 through 6 (Cohort A), followed by 480 mg every 4 weeks (Q4W) from Cycle 7 and beyond. Doses should be administered over a 30 minute period. Therapy will be continued until disease progression.
Nivolumab/Daratumumab Cohort B only: Flat dose regimen: Intravenous (IV) infusion of BMS-936558 (nivolumab) at a dose of 240 mg on Cycle 1 Day 15, followed by 480 mg every 4 weeks (Q4W) from Cycle 2 and beyond (Day 1). Doses should be administered over a 30 minute period. Therapy will be continued until disease progression.

Daratumumab

- Weight based: IV infusion of daratumumab as follows:
 - Cycle 1-2: 16 mg/kg Days 1, 8, 15, 22
 - Cycle 3-6: 16 mg/kg Days 1, 15
 - Cycle 7 & beyond: 16 mg/kg, Day 1

NIVOLUMAB/DARATUMUMAB COHORTS

Per Revised Protocol 14, Cohort A (nivolumab-daratumumab with or without pomalidomide and dexamethasone) is closed to enrollment. Cohort B (nivolumab-daratumumab and daratumumab monotherapy) is open to enrollment.

Study Phase: 1

[REDACTED]

Objectives

Primary Objective: To establish the tolerability of the combination of nivolumab and daratumumab in subjects with relapsed/refractory MM.

Secondary Objectives:

[figure not shown]
- To assess the minimal residual disease (MRD) status for MM subjects in each treatment regimen group
- To assess overall response rates (ORR) and duration of response (DOR) for MM subjects in each treatment regimen group
- To assess progression free survival (PFS) for MM subjects in each treatment regimen group
- To characterize the immunogenicity of nivolumab when administered in combination with daratumumab
- To characterize the pharmacokinetics of nivolumab when administered in combination with daratumumab

[REDACTED]

Study Design

[figure not shown]
Per revised Protocol 14, Cohort A (ND ± Pd) is closed to enrollment. Patients who are already on treatment will continue to receive study treatment as long as they derive clinical benefit and criteria for treatment discontinuation are not met.

Cohort A is closed to enrollment per Revised Protocol 14.

Per Revised Protocol 14, Cohort B (ND, D) has been added to the study and is open to enrollment.

Cohort B is open for enrollment per Revised Protocol 14.

* Split dosing is available for Cycle 1 Day 1.

Study Population: MM subjects with detectable disease (serum M-protein ≥ 0.5 g/dl, OR urine M-protein ≥ 200 mg/24-hour collection sample, OR involved serum free-light chain (sFLC) ≥ 100 mg/L provided FLC ratio is abnormal), with ECOG 0-1, who either received at least 3 prior lines of therapy (including an IMiD and a PI) or are double refractory to IMiD and PI are eligible. Excluded are MM subjects with solitary bone or extramedullary plasmacytoma as only evidence of plasma cell dyscrasia, MGUS, SMM, amyloidosis, Waldenstrom's macroglobulinemia, POEMS syndrome, active plasma cell leukemia, or subjects who received any antibody or drug specifically targeting T cell co-stimulation or checkpoint pathways or anti-CD38 monoclonal antibodies.

Study Assessments

Safety Evaluation: Adverse events will be assessed continuously during the study and for 100 days post last treatment. Adverse events will be coded using the most current version of MedDRA and reviewed for potential significance and importance. Adverse events will be evaluated according to the NCI CTCAE Version 4.0.

Stopping Rules for toxicity have been incorporated in [Section 3.1.1.1](#).

Efficacy Evaluation: Bone marrow aspirate samples for cytometry and molecular MRD assessments will be collected at specified time points and will be analyzed at Sponsor designated laboratories. For response, subjects will be evaluated using the modified International Myeloma Working Group (IMWG) criteria ([Appendix 3](#)). Serum and urine samples for efficacy laboratory assessments will be collected every 4 weeks from Cycle 1 Day 1 until disease progression. All response (\geq PR) and progression categories require 2 consecutive assessments for confirmation.

For Cohort B, all efficacy laboratory assessments (SPEP/SIFE), UPEP/UIFE, sFLC) will be done at a central laboratory, except for corrected calcium and disease status in bone marrow (ie, plasma cell percentage and clonality) which will be done locally. For Cohort A, local laboratories will be used for all efficacy assessments.

To assess potential daratumumab and nivolumab interference with serum M protein quantification, samples may be analyzed to distinguish daratumumab and nivolumab from endogenous myeloma protein (M protein).

Pharmacokinetic Evaluation: Sparse blood samples for nivolumab pharmacokinetic assessments will be collected from all subjects at specified time points.

Immunogenicity Evaluations: Blood samples to evaluate development of positive nivolumab anti-drug antibody (ADA) response will be collected at specified time points for all subjects.

Biomarker Evaluation: Biomarkers will be analyzed in peripheral blood and bone marrow aspirate to better understand how the immune microenvironment may contribute to immune evasion, the progression of multiple myeloma, and potential synergies between nivolumab and daratumumab. Residual sample material available after completion of the designated analyses may be used in the future for identification of additional predictive markers or to enhance understanding of disease biology.

Statistical Considerations

Sample Size:

Per Revised Protocol 14, Cohort A (ND ± Pd) is closed to enrollment, and Cohort B (ND and D) is open for enrollment.

The planned sample size for Cohort B (ND, D) will be approximately 60 treated subjects, randomized in a 2:1 ratio in favor of the ND arm.

This is a Phase 1/2 study and the sample size in Cohort B is not powered for statistical hypothesis testing but is designed to evaluate both safety profile and clinical benefit of nivolumab with daratumumab.

If the true toxicities incidence rate in a cohort is 20% then with 20 patients in D cohort, there is 7% chance of observing 0 - 1 toxicities (false negative rate). If the true toxicities incidence rate in a cohort is 5% rather than 20%, then there is 26% chance that there will be at least 2 toxicities in 20 subjects (false positive rate). If the true toxicities incidence rate in a cohort is 20% then with 40 patients there is 3% chance of observing 0 - 3 toxicities (false negative rate). If the true toxicities incidence rate in a cohort is 5% rather than 20%, then there is 14% chance that there will be at least 4 toxicities in 40 subjects (false positive rate).

In 2 daratumumab monotherapy studies in relapsed/refractory MM patients, including a Phase 1/2 dose escalation study (GEN501)ⁱ in patients with at least 2 lines of prior therapy and a Phase 2 study (SIRIUS)ⁱⁱ in patients with at least 3 lines of prior therapy, the ORR were 36% and 29.2% respectively.

In two combination studies in relapsed/refractory MM patients with at least 2 lines of prior therapy, including a Phase 1b study of daratumumab in combination with pomalidomide and dexamethasoneⁱⁱⁱ and a Phase 1 dose-escalation study of pembrolizumab in combination with lenalidomide and dexamethasone,^{iv} the ORR were 60%.

Table 8.1-1 summarizes the 95% exact CI for the target ORRs ranging from 30% to 80% with sample size of 20 or 40 in a cohort. At observed ORR \geq 55% with 20 subjects, the lower bound of the 95% CI is 31.5%. At observed ORR \geq 77.5% with 40 subjects, the lower bound of the 95% CI is 61.5%.

Table 8.1-2 summarizes the 95% exact CI for the target MRD-target negativity rates ranging from 10% to 30% with sample size of 20 or 40 in a cohort. At observed MRD-target negativity rates \geq 30% with 20 subjects and observed MRD-target negativity rates \geq 20% with 40 subjects, the lower bound of the 95% CI are 11.9% and 9.1% respectively compares favorably to historical MRD-target negativity rate of 8% in recurrent pretreated relapsed or refractory MM.

Endpoints:

Safety:

The primary objective is to characterize the safety and tolerability of nivolumab and daratumumab. The primary objective will be measured by:

- Number and percent of subjects that experience drug-related grade 3-4 AEs occurring up to 100 days after the last dose of study drug. [Time Frame - On a continuous basis up to 100 days after the last dose of study drug];
- Number and percent of subjects that experience drug-related grade 3-4 SAEs occurring up to 100 days after the last dose of study drug. [Time Frame - On a continuous basis up to 100 days after the last dose of study drug];
- Number and percent of subjects with clinical laboratory abnormalities by worst toxicity grade by NCI CTCAE version 4.0 (as assessed at the planned times listed in Section 5.1). [Time Frame - On a continuous basis up to 100 days after the last dose of study drug].

Efficacy: Minimal Residual Disease (MRD) negativity status, objective response rate (ORR), duration of response (DOR), progression free survival (PFS), and overall survival (OS) for all treated subjects.

Both cytometry and molecular MRD from bone marrow aspirate will be evaluated. The time point for MRD negativity status for MM subjects in the nivolumab/daratumumab cohorts is a dichotomized variable for quantifiable MRD detection.

Pharmacokinetics: Nivolumab serum concentrations at the end of a dosing interval (C_{min}) and end of study drug infusion (Ce_{inf}) will be derived from serum concentration versus time data.

Immunogenicity: The frequency of nivolumab baseline ADA positive subjects and frequency of ADA positive subjects will be provided.

Biomarker: Additional exploratory biomarker studies will be performed as described in [Section 5.7](#).

Analyses:

Safety Analyses: All recorded adverse events will be listed and tabulated by system organ class, preferred term, treatment, and coded according to the most current version of MedDRA. The incidence of adverse events will be reviewed for potential significance and clinical importance. Vital signs and clinical laboratory test results will be listed and summarized by treatment. Any significant physical examination findings and results of clinical laboratory tests will be listed. ECG results will be evaluated by the investigator and abnormalities, if present, will be listed.

Efficacy Analyses: Individual BOR, duration of response and PFS will be listed, using the modified International Myeloma Working Group Uniform Response Criteria. BOR outcomes will be tabulated by treatment. The ORR and corresponding 95% exact confidence interval will be provided by treatment. The median duration of response and PFSR at select time points and corresponding two-sided 95% confidence intervals will be estimated by Kaplan-Meier methodology, by treatment, depending on data availability. [REDACTED]

[REDACTED] Kaplan-Meier plots of PFS and overall survival will be provided by treatment. ORR, duration of response and PFS analyses will include subjects by treatment. Individual changes in the tumor burden over time may be presented graphically based on the availability of data within treatment.

MRD negativity status for MM subjects in the nivolumab/daratumumab cohorts will be evaluated by time points. The frequency of the MRD negativity status will be summarized by treatment arm. The cross tabulation of the MRD negativity status and BOR will be presented. Summary statistics of the MRD levels and their corresponding percent changes from baseline will be tabulated by planned study day by cohorts. Potential association between the first/best MRD negativity status with PFS and OS will be evaluated. Additional details will be presented in the Statistical Analysis Plan.

Pharmacokinetic Analyses: Summary statistics will be tabulated for the pharmacokinetics parameters of nivolumab by dose and study week. Pharmacokinetic concentrations of nivolumab from all subjects will be listed, and may be used in combination with other studies for exposure response or population pharmacokinetic modeling, which will be part of a separate report.

Immunogenicity Analyses: A listing will be provided of all available immunogenicity data. Additionally, a listing

[REDACTED]

[REDACTED]

[REDACTED]

[REDACTED]

[REDACTED]

[REDACTED]

[REDACTED]

TABLE OF CONTENTS

TITLE PAGE	1
DOCUMENT HISTORY	3
[REDACTED]	7
SUMMARY OF KEY CHANGES OF REVISED PROTOCOL 15.....	7
SYNOPSIS.....	12
TABLE OF CONTENTS.....	18
[REDACTED]	22
[REDACTED]	26
[REDACTED]	30
[REDACTED]	32
[REDACTED]	33
[REDACTED]	34
[REDACTED]	34
[REDACTED]	34
[REDACTED]	35
[REDACTED]	35
[REDACTED]	35
[REDACTED]	35
[REDACTED]	35
[REDACTED]	36
[REDACTED]	36
[REDACTED]	36
[REDACTED]	36
[REDACTED]	36
[REDACTED]	36
[REDACTED]	37
[REDACTED]	38
2 ETHICAL CONSIDERATIONS.....	40
2.1 Good Clinical Practice	40

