8.3.2 Secondary Endpoint(s)

8.3.2.1 Efficacy

The secondary objective relating to efficacy is to assess the preliminary antitumor activity in the combination of nivolumab and daratumumab in subjects with relapsed/refractory MM. This objective will be measured by minimal residual disease status (MRD), objective response rate (ORR), duration of response (DOR), and progression-free survival (PFS) for MM subjects in each treatment regimen group.

Minimal Residual Disease (MRD) in the Nivolumab/Daratumumab Cohorts

Both cytometry and molecular MRD from bone marrow aspirate will be evaluated.

The time point for MRD negative status for MM subjects in the nivolumab/daratumumab cohorts is a dichotomized variable for quantifiable MRD detection.

The first MRD negativity status is defined as the first negative status designation over the study as a whole, recorded between the date of first dose and the last efficacy assessment prior to subsequent therapy.

The best MRD negativity status is defined as the best status designation with the minimum MRD levels over the study as a whole, recorded between the date of first dose and the last efficacy assessment prior to subsequent therapy.

Objective Response Rate (ORR)

Best overall response (BOR) is defined as the best response designation over the study as a whole, recorded between the date of first dose and the last efficacy assessment prior to subsequent therapy.

Objective response rate is defined as the proportion of subjects who had a BOR of either partial response (PR) or complete response (CR) divided by the number of treated subjects (or response-evaluable subjects).

Duration of Objective Response (DOR)

The duration of response is defined as the time when the measurement criteria are first met for objective response until the date of documented disease progression or death, whichever occurs first. For subjects who neither progress nor die, the duration of response will be censored at the date of their last disease assessment.

Progression Free Survival (PFS)

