Progression free survival (PFS) is defined as the time between date of randomization and date of progression or death, whichever occurs first. Subjects who die without a reported prior progression will be considered to have progressed on the date of their death. Subjects who did not progress or die will be censored on the date of their last efficacy assessment. Subjects who did not have any on study efficacy assessments will be censored on the date of randomization.

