8.4.2 Efficacy Analyses

MRD negativity status for MM subjects in the nivolumab/daratumumab cohorts will be evaluated by time points. The frequency of the MRD negativity status and the best MRD negativity status will be summarized by treatment group. The cross tabulation of the MRD negativity status and BOR will be presented. Summary statistics of the MRD levels and their corresponding percent changes from baseline will be tabulated by planned study day by treatment group. Potential association between the first/best MRD negativity status with PFS and OS may be evaluated as appropriate. Additional details will be presented in the Statistical Analysis Plan.

Individual best overall response (BOR), duration of response and PFS will be listed, using the IMWG Uniform Response Criteria for Multiple Myeloma.¹⁰⁶

BOR outcomes will be tabulated by treatment group. The objective response rate (ORR) and corresponding 95% exact CI will be provided by treatment group. The median duration of response and PFS and corresponding two-sided 95% CIs will be estimated by Kaplan-Meier methodology. The analysis of overall survival would be exploratory. Kaplan-Meier plots of PFS, DOR, and OS will be provided.

Final analysis will be performed after all treated subjects have been followed for a minimum of 3 months to evaluate the efficacy endpoints.

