**PROTOCOL CA209039**

**VERSION # 3.2**

### REVISION HISTORY

Revision	Date	Revised By	Changes Made – Reasons for the Change
1.0		██████	Original issue
2.0	April 19, 2017	██████	
 
1. Include protocol amendments 04-12
 
2. Include nivolumab + ipilimumab cohorts, nivolumab + lirilumab, and 2 daratumumab + pomalidomide cohorts and update corresponding sections.
 
3. Limit biomarker analyses to PD-L1 related analyses
 
4. Add section 7.3.3 Prior Anti-Cancer Therapy
 
5. Align safety and immunogenicity sections with nivolumab core safety SAP.
 
6. Add IRRC efficacy for cHL subjects receiving nivolumab monotherapy.
 
7. Change the primary definition of PFS and DOR and use the last efficacy assessment date prior to subsequent therapy for censoring. Change initial primary definition of PFS and DOR (use the last visit date prior to subsequent therapy for censoring) to sensitivity definition.
 
8. Add in section 1 “In addition to the administrative interim analyses over the course of the study, an interim analysis is scheduled for the multiple myeloma (MM) cohorts when 30 treated patients in total from the nivolumab/daratumumab cohorts have 3 months of minimum follow-up”.
 

3.0	Feb 26, 2018	██████	
 
1. Include protocol amendments 14 dated 15-Feb-2018
 
2. Add Cohort B (nivolumab+daratumumab) vs daratumumab monotherapy [ND, D]
 

3.1	Sep 24 2019	██████	
Changed analyses population for the randomized nivolumab/daratumumab cohorts from “all treated subjects” to “all randomized subjects”.(disposition, demographics, baseline characteristics, efficacy and biomarker analyses).
 
Updated PFS, OS definitions for nivolumab/daratumumab cohorts from “time from the first dose” to “time from randomization.” Subject will be censored on randomization date for PFS when no post-baseline efficacy assessment.
 
Added protocol amendment 15 dated 23-Apr-2019

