### **Minimal Residual Disease (MRD)**

In the nivolumab/daratumumab cohorts, MRD from bone marrow aspirate will be evaluated. MRD will be assessed by Next Generational Flow Cytometry (NGF) and Next Generational Sequencing (NGS).

The timepoint MRD negativity status is a dichotomized variable for quantifiable MRD detection. MRD negativity status will be considered at  $10^{-5}$ , as per IMWG guidelines; other sensitivity levels such as  $10^{-4}$  and  $10^{-6}$  will also be considered.

The first MRD negative status is defined as the first negative status designation over the study as a whole, recorded between the date of first dose and the date of objectively documented progression or the date of subsequent therapy, whichever occurs first.

The best MRD negative status is defined as the best status designation with the lowest sensitivity level over the study as a whole, recorded between the date of first dose and the date of objectively documented progression or the date of subsequent therapy, whichever occurs first.

Time to the first MRD negative status is defined as the time from the date of randomization to the date of the first MRD negative status.

The duration of the MRD negativity is defined as the time between the date of first MRD negativity to the date of the first MRD positivity, or the date of the first objectively documented progression as assessed according to IMWG criteria or death due to any cause whichever is earlier prior to the initiation of subsequent anti-cancer therapy. Subjects who didn't have MRD positivity, and didn't progress nor die will be censored on the date of their last MRD negativity prior to the initiation of subsequent anti-cancer therapy.

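### The planned link between whole-study MRD negativity and PFS/OS from randomization has no visible protection against immortal-time bias; specify a landmark analysis

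*Protocol*

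**What the plan says.** **The analysis.** The Protocol Synopsis (Efficacy Analyses) says "Potential association between the first/best MRD negativity status with PFS and OS will be evaluated". Protocol 8.4.2 is softer: "Potential association between the first/best MRD negativity status with PFS and OS may be evaluated as appropriate". Both leave further detail to the SAP.

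**The grouping variable.** Protocol 8.3.2.1 defines first negativity as the "first negative status designation over the study as a whole, recorded between the date of first dose and the last efficacy assessment" before subsequent therapy. Best negativity is the "best status designation with the minimum MRD levels over the study as a whole". The SAP (4.2.2, Minimal Residual Disease) narrows the window for both to results "recorded between the date of first dose and the date of objectively documented progression or the date of subsequent therapy, whichever occurs first".

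**The clock.** Protocol 8.3.2.1 states: "Progression free survival (PFS) is defined as the time between date of randomization and date of progression or death, whichever occurs first". SAP 4.2.2 uses the same origin for these cohorts. For OS, the origin appears in the SAP revision history (version 3.1), which reads "Updated PFS, OS definitions for nivolumab/daratumumab cohorts from" first dose to randomization.

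**The sampling.** Under Protocol 5.4.1.1, on-study marrow is taken at C4D1, or earlier at VGPR or better, and then every 6 cycles until progression. Subjects with confirmed progression before C4D1 are sampled at that progression. SAP 6.3 counts anyone in Cohorts A and B with available MRD status as MRD-evaluable and does not require them to be event-free at any time.

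**The method.** SAP 7.5 (MRD) covers negativity by time point, time to first negativity, cumulative rates and duration of negativity. Its visible text does not mention the association with PFS or OS.

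**The concern.** MRD status here is acquired after randomization and, under the SAP window, only while the subject is progression-free. Time from randomization to the negative sample is guaranteed event-free for PFS. If it is credited to the negative group, that group gains survival time it could not have lost. Early progressors do the opposite: they are sampled at progression, can count as evaluable, and fall into the non-negative group by definition. Subjects with long PFS also have more marrow looks and so more chances of a negative result. Best status, taken over all looks, is the most exposed to this.

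At stake is how the MRD result is read. An apparent halving of the progression hazard in MRD-negative subjects could arise with no relation at all between MRD and outcome.

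**Working it through.** **Stated figures.** The documents give no figure for this association. The nearest are the exact lower 95% bounds for MRD-negativity rates, from the Beta(x, n-x+1) quantile at 0.025. For 6/20 this gives 11.89% (stated 11.9%) and for 8/40 it gives 9.05% (stated 9.1%). Both reproduce.

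**Timing.** Cycles last 28 days (Protocol 4.1.5). C4D1 falls 3 x 28 = 84 days after C1D1, about 2.76 months. Later looks are 6 x 28 = 168 days apart, about 5.5 months.

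**Early events.** With exponential PFS of median m, the share with an event before C4D1 is 1 - 2^(-2.76/m):
- m = 4: 38%, about 23 of 60
- m = 6: 27%, about 16 of 60
- m = 12: 15%, about 9 of 60

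None of these subjects can be negative at C4D1.

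**Null simulation.** N = 60 comes from the protocol. The following are assumptions:
- MRD is unrelated to outcome (true HR = 1).
- Median PFS is 4, 6 or 12 months.
- Accrual is uniform over 12 months, with minimum follow-up of 3 or 12 months (3 is the protocol's minimum).
- Negativity per look is 10-30% when conversions continue at every look. It is 20-40%, with 12-month minimum follow-up, when they can occur only at the first look.
- For OS, negativity is 20% per look, PFS medians are 4 and 6 months, and post-progression survival is exponential with median 14 or 18 months. Minimum follow-up is 12 months.
- All 60 subjects stay in the from-randomization comparison. Missed samples at progression would remove some early progressors and reduce the bias.

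Each scenario used 1,000-1,500 trials. The last column is the share of trials with z below -1.96 in favour of negative subjects, nominally 2.5%.

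| Outcome and conversion pattern | Comparison | Median HR | False benefit |
|---|---|---|---|
| PFS, every look | Ever negative, from randomization | 0.34-0.45 | 10-94% |
| PFS, every look | C4D1 landmark | 0.96-1.08 | 0.3-3.4% |
| PFS, every look | Time-dependent MRD | 0.93-1.05 | 0.4-3.5% |
| PFS, only at C4D1 | Ever negative, from randomization | 0.54-0.73 | 6-49% |
| PFS, only at C3D1 (early VGPR) | Ever negative, from randomization | 0.63-0.82 | 5-32% |
| OS, every look | Ever negative, from randomization | 0.48-0.54 | 10-15% |
| OS, every look | Time-dependent MRD | 0.63-0.68 | 4-7% |
| OS, every look | C4D1 landmark, progression-free | 0.97-1.04 | 0.2-0.4% |

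**One case in full.** With median PFS 6 months, 20% per look and 12-month minimum follow-up, 23% of subjects are ever negative. The from-randomization HR is 0.39 with 79% false benefit. The landmark gives 0.99 and 2.4%. With 3-month minimum follow-up the from-randomization figures are 0.40 and 45%.

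**Why time-dependent MRD fails for OS.** Conversion can happen only before progression. At the moment of conversion, a newly negative subject is compared with a group that includes subjects who have already progressed.

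**The case against.** The strongest reply is that no biased method is specified. The documents name no Cox model, log-rank test or baseline grouping. A time-dependent model would use the same first-negativity status and the same randomization origin, and SAP 4.2.2 already defines time from randomization to first negativity, which such a model needs. SAP text is redacted before 7.5 and after 7.7, so a method may exist there. This stands: a reader might infer that the plan commits to a biased comparison, and the documents do not support that. It does not fully answer the point. Whole-study best status is named as a predictor and has no unbiased reading as a fixed group from randomization, and the visible text offers no safeguard.

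A second reply concerns weight. Protocol 8.4.2 makes the analysis optional, the primary endpoints are safety, and Cohort B is not powered for hypothesis testing. This also stands. A reader might infer from the 5.4.1.1 heading, which calls MRD the primary efficacy assessment, that the association will be used to argue surrogacy or support the regimen. No visible text says so. The false-benefit percentages likewise presuppose a test that is not planned; they only gauge how often the artefact would look convincing.

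A third reply is that the size depends on when conversion occurs. It does, and for PFS the first-look scenarios are clearly milder. The direction was the same throughout.

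**Conclusion.** The concern holds as a gap in a supportive analysis. Comparing ever- or best-negative subjects with the rest from randomization would favour the negative group with no true association. The null PFS hazard ratio is about 0.35-0.45 if conversions continue at later looks and about 0.5-0.8 if they occur only at the first. For OS it is roughly 0.4-0.7 once the assumptions on PFS and conversion timing are widened beyond those tabulated; deaths are few (about 19-26 of 60 in the tabulated scenarios), so that range is soft.

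These sizes rest on assumed median PFS of 4-12 months, 10-40% negativity per look, exponential times and the assumed follow-up. The mechanism rests only on the documents' definitions. The primary safety endpoints and the arm-level ORR, PFS and MRD summaries are not affected.

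**What to change.** State in Protocol 8.4.2 and the SAP that any association of MRD with PFS or OS will follow these rules:

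- Use a landmark at the first on-study MRD assessment (C4D1 window), restricted to subjects alive and progression-free then, with MRD status known by the landmark and time counted from it.
- Allow time-dependent MRD status as a supporting analysis for PFS only, since it stayed biased for OS.
- Do not use whole-study best status as a baseline grouping for time-to-event outcomes. It may stay as a descriptive summary.
- Label the results as prognostic association only.

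The synopsis and 8.4.2 should also agree on whether the analysis is planned or optional.

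**Cost.** A few sentences and no new data. The analysis loses subjects with an event before C4D1, about 9-23 of 60 under the assumptions above, and ignores conversions after the landmark. It will be imprecise: with median PFS of 6 months and 20% negativity, about 44 subjects remain at risk (60 - 16) and about 9 of them are negative (0.20 x 44).
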